Hypothesis: The use of a novel adherence intervention (the AdhereTech bottle with reminders) will improve adherence to HIV medications over 12 weeks.

Primary Objective: To assess adherence to a tenofovir-based regimen over 12 weeks in patients using the AdhereTech bottle with reminders compared to the usual standard of care.

Primary Endpoint: The mean change in drug levels of tenofovir diphosphate (TFV-DP) in red blood cells using dried blood spots between week 0 and week 12 in the AdhereTech intervention group compared with the standard of care group.

Secondary Objectives:

- 1) To assess the feasibility of using the AdhereTech bottles with phone/text reminders in HIV-infected patients.
- 2) To assess the use of tenofovir diphosphate dried blood spots as a marker of HIV medication adherence in comparison with plasma tenofovir levels and self-reported medication adherence.

Secondary Endpoints:

- 1) The percentage of patients completing the 12 week AdhereTech intervention in comparison with the standard of care group.
- 2.1) Compare the mean change in TFV-DP blood spot level, TFV plasma level, and self-reported medication adherence between weeks 0 and 12 in the AdhereTech intervention and standard of care groups.
- 2.2) The mean change in HIV level and percent of patients with an HIV RNA below the level of detection between weeks 0 and 12 in the AdhereTech intervention and standard of care group.

RESEARCH PLAN:

Selection of Participants

Type of the Participant Population

This study is open to all adults who meet the following inclusion and exclusion criteria.

Inclusion and Exclusion Criteria:

Inclusion Criteria:

- Male and nonpregnant female subjects aged 18 years and older
- A diagnosis of HIV-1
- Undergoing therapy with a tenofovir-based antiretroviral regimen
- Suboptimal adherence to the tenofovir-containing HIV antiretroviral regimen over the prior 52 weeks from the time of enrollment, as evidenced by 2 HIV RNA levels above the level of

detection following an HIV RNA level below the level of detection, with no plans to change the current HIV drug regimen.

- Access to and willingness to use a cell phone to receive voice/text reminders to take HIV medications. Subjects must also agree to maintain a stable phone number and active cell phone service for the duration of the study.
- Adequate English to provide written, informed consent and to provide reliable responses to the study interview

Exclusion Criteria:

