In this pilot study, the sample size calculation is based on the null hypothesis of no difference in tenofovir-diphosphate (TFV-DP) concentrations (by dried blood spots) at baseline versus a demonstrable difference at week 12. From a simulation study (Castillo), we expect to see the same mean concentration (standard deviation) at both groups at baseline: 900 (404) fmol/punch. At 12 weeks, we expect to see a mean concentration (standard deviation) of 1332 (597) fmol/punch in arm A (adherence intervention) vs. 900 (404) fmol/punch in arm B (control). Assuming normal distribution of TFV-DP concentrations, type 1 error = 0.05, power = 80%, a sample size of 32 will be recruited per arm (64 total) based on a two-sided, two-sample t-test with equal variance. Since the data may have missing data at the last visit, we will add ~10% more participants. Therefore, the final sample size of 35 per arm (70 total) will be enrolled.

We intend to screen approximately 100 total subjects, as we assume there will be subjects who may sign the consent form, but ultimately do not participate in the study due to screen failure, not meeting inclusion/exclusion criteria, and personal choice.

Randomization will be provided by the biostatistician from Weill Cornell Medical College. The randomization list will be provided to the principal investigators.

Data Analysis:

For the primary analysis, we will compare the mean change in drug levels of tenofovir diphosphate (TFV-DP) in red blood cells using dried blood spots between week 0 and week 12 in the AdhereTech intervention group compared with the standard of care group via a two-sided t-test. If the data will not meet the normal assumption, non-parametric Wilcoxon Rank Sum test will be used to test medians between two groups.

For the secondary analyses, we will:

- Calculate the mean percentage of patients who complete the 12 week AdhereTech intervention and compare that with the percent that complete 12 weeks of follow-up in the standard of care group.
- Compare the mean change in TFV-DP blood spot level with TFV plasma level and self-reported medication adherence from weeks 0 and 12 between the AdhereTech intervention and standard of care groups.
- Compare the mean change in HIV level and median percent of patients with an HIV RNA below the level of detection from weeks 0 and 12 between the AdhereTech intervention and standard of care group.

These analyses will be performed via two-sided t-tests.

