U.S. Department of Health and Human Service, Guidelines for the Use of Antiretroviral Agents in HIV-1-Infected Adults and Adolescents, 2/12/13, available at www.aidsinfo.nih.gov

Watson A. Vitality GlowCaps Trials with Mass General Hospital and Harvard Center for Connected Health. 2008, available at <http://www.connected-health.org/events/past-events/symposium-2008/presentations.aspx>

Protocol Addendum (09-30-2016):

Addendum to Data Analysis Plan:

Due to enrollment being slower than anticipated as of August 2016 (40 of 70 total participants enrolled), we will perform an interim analysis of the tenofovir dried blood spot data for the primary endpoint. The statistician will be blinded to the participants' study group assignments. The statistician will notify us if there is a significant difference detected in the tenofovir dried blood spot levels between the two groups, but the study investigators will be blinded as to the detailed results. Such information will help us determine whether further enrollment into the study is justified. If the difference seen is $</= 5\%$ at the 5% level of significance, study enrollment will be terminated due to futility of the intervention. If the difference seen is $>/= 20\%$ at the 5% level of significance, the study will be terminated due to a significant difference demonstrating efficacy of the Intervention. If the difference is between 6-19%, study enrollment will continue as previously planned until the target sample size of 70 subjects is achieved.

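### The 2016 addendum adds an efficacy stop at the full 5% level with no adjustment of the final test, so the stated type 1 error of 0.05 is no longer assured

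*Combined protocol and SAP*

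**What the plan says.** The primary endpoint (Study Objectives and Endpoints) is "The mean change in drug levels of tenofovir diphosphate (TFV-DP) in red blood cells using dried blood spots between week 0 and week 12", compared between arms. The Sample Size Estimate sets "type 1 error = 0.05, power = 80"% for a two-sided, equal-variance, two-sample t-test. It expects a baseline mean of 900 (SD 404) fmol/punch in both arms, and at week 12 a mean of 1332 (SD 597) on the intervention and 900 (SD 404) on control. The Data Analysis section has one final test, in which the intervention group is "compared with the standard of care group via a two-sided t-test".

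The Protocol Addendum (09-30-2016) introduces an interim analysis of this endpoint because 40 of 70 participants had been enrolled by August 2016. It contains these rules:

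- Difference of 20% or more: "at the 5% level of significance, the study will be terminated due to a significant difference demonstrating efficacy of the Intervention".
- Difference of 5% or less: "study enrollment will be terminated due to futility of the intervention".
- In between: "If the difference is between 6-19%, study enrollment will continue as previously planned until the target sample size of 70 subjects is achieved".
- Reporting, by a statistician blinded to group: "The statistician will notify us if there is a significant difference detected in the tenofovir dried blood spot levels between the two groups".

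Neither the addendum nor the main text gives a reduced interim level, a spending rule or an adjusted final level.

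**The concern.** A two-sided 5% test at the interim uses the whole 0.05, and nothing is left for the final test. Continuing as planned to a second unadjusted 5% test gives chance another opportunity. A positive result at either look would then be reported as significant at 5% when the false-positive rate may be higher.

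The 20% minimum and the futility stop could offset this, but the addendum does not define them well enough to rely on. It leaves open what the percentage is relative to, whether the difference is signed, whether futility is binding, and what happens to a difference of 20% or more that is not significant. The study is a pilot, but it states a formal alpha and would end with a declaration of efficacy on this test.

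**Working it through.** **1. The plan's own figure.** For a difference of 1332 − 900 = 432 with a common SD of 597, alpha 0.05 and 80% power, the t-test needs 31 per arm, close to the stated 32. An SD of 510 (the two week 12 SDs pooled) gives 22–23 and an SD of 404 gives 14–15, so the plan appears to use 597. Power at 32 per arm is 81.3%. That design has a single look.

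**2. Two looks at 5%.** The two test statistics are approximately bivariate normal with correlation √(n/70), where n is the number of participants with data at the interim. The error is the probability that |Z| > 1.96 at either look.

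| n at interim | Overall error |
|---|---|
| 40 | 0.0806 |
| 30 | 0.0854 |
| 24 | 0.0881 |

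Forty is the number enrolled. The number with week 12 results is not given and may be lower.

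**3. Does the 20% minimum protect?** With 20 per arm, the smallest difference with p<0.05 is t(38) × SD × √(2/20), with t(38) = 2.024.

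- SD 404: 2.024 × 404 × 0.316 = 259, or 28.7% of 900.
- SD 597: 2.024 × 597 × 0.316 = 382, or 42.5% of 900.

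The 20% minimum is 180 fmol/punch, so at these SDs it never binds. It starts to bind below an SD of about 281 (base 900) or 416 (base 1332).

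**4. Simulation with the addendum's rules.** Null trials, 20 then 35 per arm, pooled t-tests. Efficacy stop: difference at least 20% and p<0.05. Futility stop: difference at most 5%. Entries are total error.

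| Reading | SD 404 | SD 597 |
|---|---|---|
| Unsigned, base 900, all others get the final test | 8.0% | 8.1% |
| Unsigned, base 900, non-significant ≥20% gets no final test | 6.5% | 5.6% |
| Unsigned, base 1332, all others get the final test | 6.7% | 7.9% |
| Signed, base 900, futility not enforced | 6.5% | 6.6% |
| Signed, base 900, binding futility, all others get the final test | 4.0% | 4.1% |
| Signed, base 900, binding futility, non-significant ≥20% gets no final test | 3.3% | 2.8% |

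In the last two rows nearly all the error is false claims of benefit. A single two-sided 5% test allows 2.5% in that tail.

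**5. The SD of the change.** The endpoint is a change, but the protocol gives only SDs at single visits. If both visits have SD 404, the change SD is 404 × √(2(1 − ρ)), where ρ is the within-person correlation; ρ = 0.5 gives 404. With a change SD of 200 and base 900 (unsigned), the error is 4.7–4.8%. If all unstopped trials continue, it passes 5% at a change SD of about 215 (base 900) or 315 (base 1332). These correspond to ρ = 1 − 215²/(2 × 404²) = 0.86 and 1 − 315²/(2 × 404²) = 0.70. Below those correlations the error exceeds 5%.

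**The case against.** The strongest reply is that 8% is not what the written rule produces. Only differences of 6–19% are said to continue, so on the literal text a non-significant difference of 20% or more gets no final test, and the error is about 5.6–6.6%. The words efficacy and futility also suggest a signed difference. With binding futility the total is then 2.8–4.1%, below 0.05. The SD of the change is unknown too, and a high within-person correlation would make the 20% minimum protective.

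All of this is correct, and it limits what can be said about size. It does not rescue the rule. The literal unsigned reading still exceeds 5%. The signed reading puts up to about 4% in the benefit tail, against 2.5% for the planned test. A two-sided test run by a statistician blinded to group fits an unsigned difference at least as well. An error rate that depends on choices the plan does not make is not controlled.

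A second reply concerns overestimation after an early stop. With a true effect of 20% of 900, the mean estimate at an efficacy stop under the present rule is about 37% (SD 404) to 52% (SD 597). A stricter interim boundary raises this, to about 45–64% at p<0.0061, although such stops are rarer. Overestimation is therefore a reason to interpret any early stop with care. It is not an argument for the boundary.

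Pilot status is a fair point about consequences, but the protocol itself claims a 0.05 error rate.

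**Conclusion.** The concern holds. That no adjustment is stated is certain from the text, and the 0.05 in the sample size section is no longer assured. The size of the inflation is conditional. It is about 8% on an unsigned reading with percentages of 900, a change SD of 404–597, 20 then 35 per arm, and a final test for every unstopped trial. It is about 5.6–6.6% if large non-significant differences get no final test. It is at or below 5% in total if the change SD is small enough for the 20% minimum to bind, or if the difference is signed and futility is binding, though at SD 404–597 the signed reading still exceeds 2.5% for false benefit. This should be corrected before any efficacy claim rests on either look.

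**What to change.** Replace the 5% level in the efficacy stop with a stated boundary and its matching final level. Either of these would do:

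- **Lan-DeMets, O'Brien-Fleming type:** interim p<0.0061 and final p<0.0481 at 40/70, recomputed for the number who actually have week 12 data (0.0012 and 0.0496 at 30/70).
- **Haybittle-Peto:** interim p<0.001 and final p<0.0499.

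In simulation with the addendum's rules, both bring the error back to about 5%.

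The same edit must state:

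- (a) that a difference of 20% or more that misses the boundary continues to 70 and gets the final test;
- (b) what the percentage is relative to;
- (c) whether the difference is signed;
- (d) whether the futility stop is binding.

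**Cost.** Only addendum wording changes, with no added participants, visits or assays. An early efficacy stop becomes harder to reach. At a difference of 432, SD 597 and 32 per arm (the planned number after allowing for missing data), power is 81.3% with a single test, 80.9% with the Lan-DeMets pair and about 81% with Haybittle-Peto, provided item (a) is adopted. Without item (a), power with the Lan-DeMets pair falls to about 30%, so the boundary should not be changed alone.
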